10.6.1 HANDLING OF WITHDRAWALS OF CONSENT

Patients may withdraw consent to participate in this study at any time without penalty or loss of benefits to which the patient is otherwise entitled. When a patient wishes to withdraw consent, it is important to distinguish between withdrawing their consent for a particular study procedure or visit versus withdrawing their consent from the study entirely. The Investigator should discuss with the Medical Monitor whether selective withdrawal of consent for specific procedures should disqualify the patient from further participation in the study.

10.7 ANCILLARY TREATMENTS

The use of premedications prior to administration of mRNA-2416 is at the discretion of the treating investigator. If the treating physician decides to premedicate their patients, it is recommended to do so prior to the second and subsequent injections, and to follow local institutional guidelines for premedication with montelukast, H-1 and H-2 antagonists. Per exclusion criteria 7, immunosuppressive doses of systemic steroids or absorbed topical steroids (doses >10 mg prednisone daily equivalent) are not allowed within 2 weeks before the start of study treatment.

If any patient develops an injection related reaction (IRR) despite premedication with montelukast, H-1 and H-2 antagonists, please contact the Moderna Medical Monitor regarding continued treatment with mRNA-2416. If treatment is to be continued, it is recommended to escalate the pretreatment regimen as per institutional guidelines.

If any patient develops a Grade 3 or above IRR, then that patient must be discontinued from further injections with mRNA-2416. If ≥ 2 patients experience Grade 3 or above IRR, then a mandatory primary prophylaxis premedication regimen including montelukast, H-1 and H-2 antagonists will be instituted after discussion and agreement among principal investigators and Moderna Medical Monitor.

Rescue Medications and Supportive Care

Patients should receive appropriate supportive care measures as deemed necessary by the treating investigator. Suggested supportive care measures for the management of AEs with potential immunologic etiology are outlined, along with the dose modification guidelines, in Section 10.3 and Appendix E. Where appropriate, these guidelines include the use of oral or IV treatment with corticosteroids, as well as additional anti-inflammatory agents if symptoms do not improve with administration of corticosteroids. Note that several courses of steroid tapering may be necessary as symptoms may worsen when the steroid dose is decreased. As a result of immune-mediated AEs that could potentially be experienced by patients on durvalumab, steroids and other immunosuppressant rescue medication has to be made available to this patient population.

10.8 CONCOMITANT THERAPY

The investigator must be informed as soon as possible about any medication taken from the time of screening until the end of the clinical treatment phase of the study including the 90-day Safety Follow-up Period following the last dose of study drug.

Any medication or vaccine, including over-the-counter or prescription medicines, vitamins, pro-biotics, and/or herbal supplements that the patient is receiving at the time of enrollment or receives during the study must be recorded along with the following:

- Reason for use
- Dates of administration including start and end dates
- Dosage information including dose, unit and frequency

Patients must be instructed not to take any medications, including over-the-counter products, without first consulting with the investigator.

Restricted, prohibited, and permitted concomitant medications are described in [Table 4](#) and [Table 5](#). Refer also to the Dose Modification and Toxicity Management Guidelines (see [Section 10.4](#)).

Table 4: Prohibited concomitant medications

Prohibited medication/class of drug:	Usage:
For all treatment arms	
Any investigational anti-cancer therapy other than those under investigation in this study	Should not be given concomitantly whilst the patient is on study treatment
mAb against PD-1, or PD-L1 other than those under investigation in this study	Should not be given concomitantly whilst the patient is on study treatment
Any concurrent chemotherapy, radiotherapy, immunotherapy, or biologic or hormonal therapy for cancer treatment other than those under investigation in this study	Should not be given concomitantly whilst the patient is on study treatment. (Concurrent use of hormones for non-cancer-related conditions [eg, insulin for diabetes and hormone replacement therapy] is acceptable. Local treatment of isolated lesions, excluding target lesions, for palliative intent is acceptable [eg, by local surgery or radiotherapy])
Live attenuated vaccines	Should not be given through 30 days after the last dose of IP

Prohibited medication/class of drug:	Usage:
Any substrates to CYP3A4, CYP2C19, and CYP1A2.	Should be used with caution through to 90 days after the last dose of study treatment
For the durvalumab treatment arm only	
Immunosuppressive medications including, but not limited to, systemic corticosteroids at doses exceeding 10 mg/day of prednisone or equivalent, methotrexate, azathioprine, and tumor necrosis factor- α blockers	
Should not be given concomitantly or used for premedication prior to the infusions. The following are allowed exceptions:
 
Use of immunosuppressive medications for the management of IP-related AEs,
 
Use in patients with contrast allergies.
 
In addition, use of inhaled, topical, and intranasal corticosteroids is permitted.
 
A temporary period of steroids will be allowed if clinically indicated and considered to be essential for the management of non-immunotherapy related events experienced by the patient (eg, chronic obstructive pulmonary disease, radiation, nausea).

EGFR TKIs	
Should not be given concomitantly.
 
Should be used with caution in the 90 days post last dose of durvalumab.
 
Increased incidences of pneumonitis (with third generation EGFR TKIs) and increased incidence of transaminase increases (with 1st generation EGFR TKIs) has been reported when durvalumab has been given concomitantly.

Herbal and natural remedies which may have immune-modulating effects	Should not be given concomitantly unless agreed by the Sponsor

Abbreviations: AE, adverse event; CYP, cytochrome P450; EGFR, epidermal growth factor receptor; IP, investigational product; mAb, monoclonal antibody; PD-1, programmed cell death protein 1; PD-L1, programmed death - ligand 1; TKI, tyrosine kinase inhibitor

Table 5: Supportive medications

Supportive medication/class of drug:	Usage:
Concomitant medications or treatments (eg, acetaminophen or diphenhydramine) deemed necessary to provide adequate prophylactic or supportive care, except for those medications identified as “prohibited,” as listed above	To be administered as prescribed by the investigator
Best supportive care (including antibiotics, nutritional support, correction of metabolic disorders, optimal symptom control, and pain management [including palliative radiotherapy to non-target lesions, etc])	Should be used, when necessary, for all patients
Inactivated viruses, such as those in the influenza vaccine	Permitted

10.9 MANAGEMENT OF CLINICAL SUPPLIES

mRNA-2416 will be supplied by the Sponsor as solution for intratumoral injection in 2-mL glass vials. mRNA-2416 must be stored at -20°C. Detailed information regarding the storage and preparation of the mRNA-2416 will be provided in the Pharmacy Manual.

Durvalumab will be supplied by the Sponsor as a 500-mg vial solution for infusion after dilution (50 mg/mL). Durvalumab vials are to be stored at 2°C to 8°C (36°F to 46°F) and must not be frozen. Drug product should be kept in original packaging until use to prevent prolonged light exposure. A temperature log will be used to record the temperature of the storage area. Temperature excursions outside the permissible range listed in the clinical supply packaging are to be reported to the monitor upon detection. A calibrated temperature monitoring device will be used to record the temperature conditions in the drug storage facility. Storage conditions stated in the IB may be superseded by the label storage.

mRNA-2416 and durvalumab must be stored in a restricted access area under the storage conditions indicated in the Pharmacy Manual.

10.10 RADIOLOGIC ASSESSMENTS

For the purpose of this clinical trial, the following imaging will be acquired at Screening for a baseline tumor assessment and on study:

- CT (with contrast) or magnetic resonance imaging (MRI) of the chest, abdomen and pelvis
- CT (with contrast) or MRI of the neck, if clinically indicated
- Bone scan if clinically indicated

- PET-CT (for lymphoma)

All patients will have tumor assessments performed within 28 days prior to C1D1, every 56 days from C1D1 (\pm 7 days), and during Disease Progression Follow-up Period at 90 and 180 days following the end of treatment (\pm 30 days).

At screening, all patients will undergo CT with IV contrast of the chest, abdomen and pelvis. MRI should only be used to evaluate sites of disease that are not adequately imaged by CT. If a patient is intolerant of iodine-based contrast agents, CTs may be performed without contrast. MRI may be used to evaluate sites of disease where a CT without IV contrast is not adequate. Visible skin lesions and easily palpable subcutaneous tumors may be measured by physical examination using a ruler or calipers. Bone scans should be performed within past 60 days prior to Cycle 1 Day 1. If the baseline bone scan is positive, scans should be repeated at Cycle 3 Day 1, Cycle 5 Day 1, at the end of Cycle 6, and during Disease Progression Follow-up Period at 90 and 180 days following the end of treatment (\pm 30 days).

For optimal evaluation of patients, the same methods of assessment and technique should be used to characterize each identified and reported lesion at baseline and during follow-up. Target lesions should be selected and measured as per RECIST guidelines (see [Appendix C](#) and [Appendix D](#)).

At the investigator's discretion, imaging studies may be repeated at any time if disease progression is suspected. Due to the possibility of pseudoprogression, patients will be permitted to continue with treatment beyond initial RECIST 1.1 or Cheson defined disease progression as long as they meet the following criteria:

- If, in the opinion of the investigator, he/she is continuing to receive clinical benefit as defined by:
 - Absence of clinical symptoms and signs (including worsening of laboratory values) indicating disease progression
 - No decline in ECOG performance status
 - Absence of rapid progression of disease or of progressive tumor at critical anatomical sites (e.g., cord compression) requiring urgent alternative medical intervention.
 - Subject is tolerating study drug

All decisions to continue treatment beyond disease progression must be discussed with the Sponsor/Medical Monitor and documented in the study records. Disease progression will be confirmed after at least 4 weeks per irRC/LYRIC. If disease progression is confirmed per irRC/LYRIC, the patient will discontinue study therapy. The local investigator's assessment will be used for the analysis of response according to both RECIST 1.1 and irRC/Lyric, and for treatment decision making (study discontinuation due to PD as per irRC). Patients experiencing progressive disease per RECIST v. 1.1 criteria may continue to be treated according to irRC guidelines until progression is documented via irRC. Imaging data may be centrally collected and checked for quality by an imaging Contract Research Organization (CRO) designated by Moderna. The local investigator's assessment will be used for the data analysis and for treatment decision making. Central review of the imaging data may be performed if deemed necessary.

10.11 OPTIONAL DIGITAL PHOTOGRAPHY

In addition to radiological imaging techniques, photographs of visible cutaneous lesions are recommended. Optional digital photograph(s) will be taken of all visible injected tumor(s) and non-injected tumors and of any remaining visible local reactions in or around the injected lesion(s) for exploratory analysis.

10.12 PHARMACOKINETICS AND IMMUNOGENICITY

Blood samples will be collected from all enrolled patients for the determination of serum mRNA-2416 concentrations at the time points indicated in [Table 6](#). Blood samples will also be collected to assess the potential for immunogenicity in each treatment cycle in the peripheral circulation at the time points indicated in [Table 6](#). Immunogenicity to the study treatment will be assessed by monitoring the formation of anti-PEG and anti-OX40L antibodies. Antibodies may be further characterized and/or evaluated for their ability to neutralize the activity of the study treatment.

10.12.1 DURVALUMAB PHARMACOKINETICS

Blood samples will be collected at the time points indicated in [Table 6](#) and may be used to assess durvalumab serum concentration.

If emerging data from this study are consistent with the existing data from other durvalumab clinical trials, durvalumab PK sampling may be reduced or discontinued.

10.13 BIOMARKERS

In this study, biomarker samples will be collected per Tables 6, 7,8 and 9. The biomarker analysis will be used to investigate the effect of mRNA-2416, as well as to determine how the markers are associated with clinical outcome. Immune responses will be studied in the peripheral circulation and in tumor biopsy specimens. Tumor biopsies will be examined using methods such as immunohistochemistry, quantitative immunofluorescence, RNA sequencing and/or electrochemiluminescence (ECL) assays to evaluate changes in key immune pathway axes, such as PD-L1/PD-1 and OX40L/OX40, as well as characterization (eg, phenotype, distribution, and activation) of tumor infiltrating lymphocyte and myeloid populations. Cytokines may also be examined in both tumor and blood tissues using methods such as RNA sequencing and enzyme-linked immunosorbent assay (ELISA)/ ECL assays, respectively.

The goal of the biomarker assessments is to provide supportive data for the clinical study; however, there may be circumstances when a decision is made to stop a collection or not perform or discontinue an assessment (eg, inadequate sample number, sample quality or assay issues that preclude analysis, or impossibility to perform correlative analyses). Therefore, sample collection and/or assessment may be omitted at the discretion of the Sponsor.

The sample collection information must be entered on the appropriate sample collection log eCRF page(s). Sample details including volume and instructions for the collection, handling, and shipment of samples are outlined in the laboratory manual for the study.

Table 6: Sampling schedule for Pharmacokinetics, Immunogenicity, and Cytokine Profiling

Cycle	Day	Scheduled Time (Sampling Window)	Purpose ^a
1	1	Pre-dose of Cycle 1 Day 1	PK, Cytokines, IG
1	1	3 h from start of injection (\pm 10 min)	PK, Cytokines
1	1	6 h from start of injection (\pm 30 min)	PK, Cytokines
1	2	24 h from start of injection (\pm 60 min)	PK, Cytokines
1	8	168 h from start of injection (\pm 24 h)	PK, Cytokines
1	15	Pre-dose of Cycle 1 Day 15	IG
2	1	Pre-dose of Cycle 2 Day 1	PK, Cytokines, IG, mAb PK
3	1	Pre-dose of Cycle 3 Day 1	IG
3	15	Pre-dose of Cycle 3 Day 15	IG
4	1	Pre-dose of Cycle 4 Day 1	IG
5	1	Pre-dose of Cycle 5 Day 1	IG
6	1	Pre-dose of Cycle 6 Day 1	IG
6	15	Pre-dose of C1D15	IG
EOT		Anytime	IG
Unscheduled		Anytime when needed	PK, Cytokines, IG, mAb PK

Abbreviations: EOT, end of treatment; FU, follow-up; IG, immunoglobulin; PEG, polyethylene glycol, mAb, monoclonal antibody (durvalumab).

a. IG analyte is anti- PEG and -OX40L anti-drug antibody

10.13.1 TUMOR BIOPSIES

Patients enrolled in the Biopsy Cohort Enrichment ([Section 8.2.2](#)) and all patients in the Dose Expansion period must consent to pre-treatment and on-treatment tumor biopsies. For all patients, every attempt to biopsy the same lesion pre- and post-dose should be made to minimize inter-lesion variability. If, for any reason, a lesion that has been biopsied pre-dose is not amenable to intratumoral injection with study drug, a different lesion or lesions may be injected, providing that the lesion can be biopsied post-dose.

For all biopsies of tumors that have received intratumoral injections, the biopsy site should be the same as, or as close as possible to, the site of injection of mRNA-2416.

Biopsies of superficial lesions may be performed by punch biopsy or by excision biopsy, at the discretion of the investigator. For visceral lesions, a core biopsy may be obtained under imaging guidance preferably using an 18-gauge biopsy needle. For optimal results, 4 to 6 passes are requested, if feasible. Fine needle

aspiration of cells from tumors will not be suitable for analysis. Institutional standard operating procedures and safety procedures should be used for each biopsy procedure. Biopsied tissue samples should be placed immediately into formalin fixative, and labeled, processed, and shipped as outlined in the mRNA-2416-P101 Laboratory Manual.

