 - a. Dose Escalation and Dose Confirmation Periods: Histologically- or cytologically-confirmed advanced/metastatic solid tumor or lymphoma by pathology report and who has received, or been intolerant to, all approved therapies. Advanced solid tumors (i.e. including but not limited to melanoma, breast, head and neck squamous cell) and lymphomas (i.e. including by not limited to diffuse large B cell lymphoma) of any type are eligible for enrollment.
 - b. Dose Expansion Period: Histologically or cytologically confirmed diagnosis of: epithelial cancer of the ovary, fallopian tube, or peritoneum which is platinum resistant or platinum refractory. Patients must have received at least 2 prior lines of therapy. Patients with known BRCA mutation positive must have been treated with and progressed on at least 1 prior PARPi (poly(ADP-ribose) polymerase inhibitor)
3. No limit to the number of prior therapies
 - a. Patients who refuse standard treatments may also be considered provided that he/she has been made aware of all therapeutic options and it is documented in the study records.
4. Lesions for intratumoral injection and biopsies:
 - a. Dose Escalation: A minimum of one lesion that is easily accessible for injection where easily accessible is defined as a cutaneous or subcutaneous mass that is palpable and/or visualizable by ultrasound
 - b. Dose Confirmation: A minimum of one visceral lesion injectable with ultrasound or computer tomography (CT) guidance and that is not encasing or abutting major vascular structures or are in a location that are considered high risk for AEs by the enrolling physician
 - c. Dose Expansion: A minimum of one lesion amenable to injection (either non-visceral or visceral). Patients must have a tumor lesion amenable to biopsy and consent to a pre-treatment and an on-treatment biopsy. For patients with only one lesion amenable to injection, biopsy, and RECIST assessment, the lesion must be ≥ 2 cm.
 - d. Biopsy Cohort Enrichment: Patients must have a tumor lesion amenable to biopsy and consent to a pre-treatment and an on-treatment biopsy
5. All lesion(s) targeted for the initial injection must be ≥ 0.5 cm on longest diameter, be at least 5 mm thick, and have distinct borders based on exam or imaging, not close to critical structures such as major vessels, nerves, or airways
6. Patients must have measurable disease as determined by RECIST v1.1 (solid tumors) or Cheson 2014 criteria (lymphomas).

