10.13.3 DOSE EXPANSION BIOPSY COLLECTION PLAN

For all patients in dose expansion, collection of newly obtained tumor samples during screening and at 1 of the time points as specified below is required unless not medically feasible and agreed by the Sponsor. An additional optional biopsy at the time of treatment response or disease progression is also requested if medically feasible.

For all patients in dose expansion, biopsies at screening should be performed on a lesion which is planned for injection of study treatment, as well as a distal non-visceral lesion which is not planned for injection of study treatment if medically feasible. Similarly, the on-treatment biopsies should be performed on a lesion which has been injected with study treatment, as well as on a distal non-visceral lesion which has not been injected with study treatment if medically feasible. Every attempt should be made to biopsy the same injected and distal lesions at all time points.

Patients in dose expansion will be assigned to biopsy groups which each have a different timepoint for the on-treatment biopsies, as specified below.

Arm A Expansion Biopsy Group D:

Within 14 days pre-dose Cycle 1 Day 1: A baseline tumor biopsy of a lesion that is planned for intratumoral injection, as well as a distal non-visceral lesion which is not planned for injection if medically feasible.

24 to 48 hours post-dose Cycle 1 Day 1: Tumor biopsy of the injected tumor lesion, as well as a distal non-visceral lesion which has not been injected with study treatment if medically feasible. The biopsy of the injected lesion should include or be as close as possible to the injection site.

Arm A Expansion Biopsy Group E:

Within 14 days pre-dose Cycle 1 Day 1: A baseline tumor biopsy of a lesion that is planned for intratumoral injection, as well as a distal non-visceral lesion which is not planned for injection if medically feasible

Pre-dose Cycle 2 Day 1: Tumor biopsy of the injected tumor lesion, as well as a distal non-visceral lesion which has not been injected with study treatment if medically feasible. The biopsy of the injected lesion should include or be as close as possible to the injection site.

Arm B Expansion Biopsy Group F:

Within 14 days pre-dose Cycle 1 Day 1: A baseline tumor biopsy of a lesion that is planned for intratumoral injection, as well as a distal non-visceral lesion which is not planned for injection if medically feasible.

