8.1. Overall Response Rate

ORR is defined as the proportion of patients whose best overall response is partial response or better based on each corresponding criterion. If data allow, ORR may be summarized with Clopper-Pearson 95% confidence intervals (CI). No confirmation is required for partial response or better.

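### A superficial RECIST target lesion may be removed by excision at the on-treatment biopsy, and no scoring rule stops that removal from counting as a response in the Phase II primary endpoint

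*Protocol*

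**What the plan says.** **Biopsy method.** Protocol 10.13.1: "Biopsies of superficial lesions may be performed by punch biopsy or by excision biopsy, at the discretion of the investigator". The sentence carries no exception for target lesions. Visceral lesions are sampled by core needle.

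**Who is biopsied.** Protocol 10.13.1 says that "all patients in the Dose Expansion period must consent to pre-treatment and on-treatment tumor biopsies". Section 10.13.3 qualifies this: collection "is required unless not medically feasible and agreed by the Sponsor". Section 10.13 also lets the Sponsor drop a collection.

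**Which lesion.** Under 10.13.3, "the on-treatment biopsies should be performed on a lesion which has been injected with study treatment", plus a distal lesion where feasible. Inclusion criterion 4c in Section 9.1 provides for complete overlap: "For patients with only one lesion amenable to injection, biopsy, and RECIST assessment, the lesion must be ≥ 2 cm". Section 10.1 allows the injected expansion lesion to be superficial, and Section 10.10 allows skin and palpable subcutaneous lesions to be measured with a ruler or calipers. A superficial lesion can therefore be a target lesion.

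**When.** On-treatment expansion biopsies are at 24 to 48 hours after Cycle 1 Day 1 (Groups D and F), pre-dose Cycle 1 Day 15 (Group G) or pre-dose Cycle 2 Day 1 (Groups E and H). Section 10.10 puts the first response assessment 56 ± 7 days from Cycle 1 Day 1.

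**Scoring.** Appendix D sets PR at a fall of at least 30% in the sum of target diameters. SAP 8.1 adds: "No confirmation is required for partial response or better". Section 10.10 makes the investigator's assessment the one analysed.

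**Protection elsewhere.** Table 4 in Section 10.8: "Local treatment of isolated lesions, excluding target lesions, for palliative intent is acceptable". Biopsy has no matching clause.

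**The concern.** The Phase II primary endpoint is an unconfirmed, investigator-assessed response rate in two uncontrolled arms with null rates of 0.05 and 0.10. A procedure required by the protocol can take out part or all of what that endpoint measures, between the baseline measurement and the first response scan. The plan accepts that local treatment of a target lesion would spoil the measurement, since Table 4 excludes it, but it leaves the same opening in the biopsy section.

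If removal is read as shrinkage, the bias can only raise the response rate. It can open Stage 2 and add to the success counts of 4 of 27 and 8 of 41. A confirmation scan would not correct it, because an excised lesion stays absent.

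**Working it through.** **1. Timing.** Pre-dose Cycle 2 Day 1 falls 28 days after Cycle 1 Day 1, or 30 with the +2-day window. The earliest first scan is 56 − 7 = 49 days after Cycle 1 Day 1. So for a patient on schedule, the latest scheduled on-treatment biopsy precedes the first response scan by at least 49 − 30 = 19 days.

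**2. Effect on the sum of diameters.** Removing one of k equal target lesions lowers the sum by 1/k:

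| k | Change in sum | Meets 30%? | Growth of the remaining targets that still leaves a PR |
|---|---|---|---|
| 1 | −100% | yes | none remain |
| 2 | −50% | yes | up to 70/50 − 1 = 40% |
| 3 | −33% | yes | up to 70/66.7 − 1 = 5% |
| 4 | −25% | no | – |

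With unequal lesions, an excised 20 mm lesion reaches the threshold if 20/(20 + x) ≥ 0.30, that is, if the other target diameters sum to x ≤ 46.7 mm. In every row the patient must also have no new lesion and no unequivocal non-target progression. For k = 1 the result is a CR only if non-target disease has cleared as Appendix D requires; otherwise it is a PR.

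**3. The plan's own figures (Protocol 13.2).** Inputs: Arm A goes on with at least 1 of 13 and is active with at least 4 of 27, for rates 0.05 against 0.20. Arm B goes on with at least 2 of 15 and is active with at least 8 of 41, for rates 0.10 against 0.25. The stated one-sided alpha is 0.05 and the power 0.80.

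P(active | p) = Σ over x ≥ r₁ of P(X₁ = x) · P(X₂ ≥ r − x), where X₁ ~ Bin(n₁, p), X₂ ~ Bin(n − n₁, p), r₁ is the Stage 1 threshold and r the final threshold.

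Arm A at p = 0.05, for x = 1, 2, 3, then x ≥ 4: 0.3512·0.0301 + 0.1109·0.1530 + 0.0214·0.5123 + 0.0031 = 0.0416. Power at 0.20 is 0.8011. Arm B gives 0.0430 at p = 0.10 and power 0.8029 at 0.25. The plan's figures are reproduced.

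**4. Sensitivity to spurious response.** The documents give no frequency, so the added rate at the null is an assumption, shown over a range:

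| Added points (assumed) | Arm A: p, P(active) | Arm B: p, P(active) |
|---|---|---|
| 0 | 0.05, 0.042 | 0.10, 0.043 |
| 1 | 0.06, 0.072 | 0.11, 0.068 |
| 2 | 0.07, 0.111 | 0.12, 0.101 |
| 5 | 0.10, 0.271 | 0.15, 0.244 |

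**5. One spurious responder in Stage 1, all other patients at the null.**
- Arm A: the gate is met with certainty, against 1 − 0.95¹³ = 0.487 otherwise, and P(active) is 0.139.
- Arm B: the gate is met if at least one of the other 14 responds, 1 − 0.90¹⁴ = 0.771, against 0.451 otherwise, and P(active) is 0.097.

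**The case against.** Several parts of the plan make this less likely than the permission alone suggests, and they stand.

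- **Screening excision is largely self-defeating.** Sections 10.13.1 and 10.13.3 ask for the same lesion to be biopsied before and after dosing. Injected lesions are to be sampled at or near the injection site. A lesion fully removed at screening can be neither injected nor re-sampled. A reader might infer that the screening biopsy feeds the bias equally; the documents do not support that.
- **Not every patient is exposed.** Biopsy can be waived or omitted, visceral lesions get a core biopsy, and distal sampling depends on feasibility.
- **The 2 cm rule in criterion 4c** suggests that the authors expected a sole lesion to survive its biopsy. It does not prohibit excision. Removing the only injectable lesion would, however, meet a reason in Section 10.5 for stopping therapy, which makes the k = 1 case unattractive.
- **The remaining disease must cooperate.** At k = 3 the other two targets may grow by only 5% in total, in platinum-resistant or platinum-refractory disease.
- **Appendix D is a summary.** A reader might infer that it requires a removed lesion to be scored as disappeared. It says nothing about surgical removal and points to the full RECIST publication. The supportable statement is that neither document gives a rule.
- **Detection.** The SAP lists target-lesion assessments and procedures, and Section 10.10 allows central review if thought necessary. These could reveal a case, but they do not change how it is scored.
- **Stage 2 is not automatic on one reading.** Section 8.2.5 says the sample may be expanded after a response, whereas Section 13.2 says the study will proceed.

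What remains is excision of a superficial target lesion at the on-treatment biopsy. The same-lesion rule does not prevent it there, apart from the optional later biopsy.

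**Conclusion.** The gap is real but narrow. The plan permits an on-treatment excision of a superficial target lesion before the first response scan, and nothing in Appendix D or SAP Section 8 stops the resulting fall in the sum from being recorded as an unconfirmed response. The conclusion rests on four conditions: the lesion is a target, there are few targets (up to three if equal in size), the remaining disease is close to stable, and there is no new lesion or non-target progression.

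The size is unknown. The rise to 0.111 and 0.101 shows what any 2-point inflation of the null rate would do to these designs; it should not be read as an estimate of how often biopsies would cause one. What follows directly from the design is its sensitivity: a single such patient settles the Arm A Stage 1 gate, and the final thresholds are only 4 and 8 responses. That justifies a wording change. It does not support a claim that the primary endpoint is generally invalid.

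**What to change.** 1. **Protocol 10.13.1 and 10.10.** State that a lesion to be sampled by excision may not be chosen as a RECIST target lesion, and that a target lesion is not sampled by excision. This brings biopsy into line with the target-lesion protection in Table 4.
2. **SAP Section 8.** State that a target lesion removed by excision is scored not evaluable at all later time points, so that its removal cannot support a PR or CR. The not-evaluable category already exists there for RECIST 1.1.

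A new baseline measurement after the screening biopsy is not recommended. For visceral targets sampled by core it would need a repeat scan, and moving a CT-measured lesion to calipers would conflict with the same-method rule in Section 10.10.

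The cost is wording only, with no added patients or procedures. The downside is somewhat less tissue from a few superficial target lesions and possibly a few responses that become not evaluable. With the rule in place, this route adds nothing to the null response rate, and the designs keep their attained error rates of 0.042 and 0.043.
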